9. STUDY CALENDAR.....	17

A Randomized Clinical Trial of the LYMPHA procedure for the Prevention of Lymphedema
after Axillary Lymphadenectomy

10. MEASUREMENTS.....	18
10.1 PRIMARY OUTCOME MEASURE: INCIDENCE OF LYMPHEDEMA.....	18
10.2 SECONDARY OUTCOMES: OTHER METRICS OF LYMPHEDEMA	18
10.3.3 RESPONSE IS NOT THE PRIMARY OUTCOME.....	18
11. REGULATORY CONSIDERATIONS.....	18
11.1 INSTITUTIONAL REVIEW OF PROTOCOL	18
11.2 DATA AND SAFETY MONITORING PLAN	19
11.3 DATA MANAGEMENT PLAN.....	19
12. STATISTICAL CONSIDERATIONS.....	19
12.1 STATISTICAL DESIGN.....	19
12.2 PRELIMINARY ASSESSMENT	20
12.3 DESCRIPTIVE STATISTICS AND EXPLORATORY DATA ANALYSIS.....	20
12.4 PRIMARY ANALYSIS	21
12.4.1 ANALYSIS POPULATION	21
12.5 SECONDARY ANALYSIS	21
12.5.1 ANALYSIS POPULATION	21
12.6 SAMPLE SIZE	22
12.7 CRITERIA FOR FUTURE STUDIES	22
13. REFERENCES	23
APPENDICES.....	25
APPENDIX A: PARTICIPANT ELIGIBILITY CHECKLIST	25
SUPPORTING DOCUMENTATION*	25

[figure not shown]
A Randomized Clinical Trial of the LYMPHA procedure for the Prevention of Lymphedema after Axillary Lymphadenectomy

PROTOCOL SYNOPSIS

TITLE	A Randomized Clinical Trial of the LYMPHA procedure for the Prevention of Lymphedema after Axillary Lymphadenectomy
STUDY PHASE	Randomized Clinical Trial
INDICATION	Unilateral axillary lymphadenectomy related to breast cancer
INVESTIGATIONAL PRODUCT OR PROCEDURE	Immediate lymphatic reconstruction (LYMPHA procedure)
PRIMARY OBJECTIVE(S)	To determine if the use of LYMPHA in breast cancer patients undergoing axillary lymphadenectomy will reduce the risk of limb lymphedema as determined based on the fulfilment of at least one of the following three criteria: (1) More than 10% increase in the relative excess volume of the affected limb; (2) More than 50% time delay of ICG migration from the injection points to the axilla of the affected upper limb in comparison with the contralateral healthy upper limb; or (3) Aggravation of one or more stages in Yamamoto's classification of the dermal back flow and morphology of the lymphatic collectors.
SECONDARY OBJECTIVE(S)	To determine if the use of LYMPHA in breast cancer patient undergoing axillary lymphadenectomy will reduce the risk of limb lymphedema as measured by other metrics of clinical lymphedema, including limb volume, skin thickness measurements, and bioimpedance spectroscopy. To determine if the use of LYMPHA in breast cancer patients undergoing axillary lymphadenectomy will improve quality of life, as measured by limb-lymphedema-specific quality of life (LYMQOL) tool.
TREATMENT SUMMARY	Patients undergoing unilateral axillary lymphadenectomy will undergo the immediate lymphatic reconstruction (LYMPHA) at the same time.
SAMPLE SIZE	100 patients (randomized)
STATISTICAL CONSIDERATIONS	Fisher's exact test and general linear mixed models

A Randomized Clinical Trial of the LYMPHA procedure for the Prevention of Lymphedema after Axillary Lymphadenectomy

SCHEMA

Key:

LYMQOL = limb-lymphedema-specific quality of life
LYMPHA = LYmphatic Microsurgical Preventive Healing Approach

A Randomized Clinical Trial of the LYMPHA procedure for the Prevention of Lymphedema after Axillary Lymphadenectomy

LIST OF ABBREVIATIONS AND DEFINITION OF TERMS

LYMQOL	limb-lymphedema-specific quality of life
LYMPHA	LYmphatic Microsurgical Preventive Healing Approach
ICG	Indocyanine Green
ALND	Axillary Lymph Node Dissection

A Randomized Clinical Trial of the LYMPHA procedure for the Prevention of Lymphedema after Axillary Lymphadenectomy

1. OBJECTIVES

1.1. Primary Objective

To determine if the use of LYMPHA in breast cancer patients undergoing axillary lymphadenectomy will reduce the risk of limb lymphedema as measured by ICG lymphangiography and by relative limb volume measurement.

1.2. Secondary Objectives

To determine if the use of LYMPHA in breast cancer patient undergoing axillary lymphadenectomy will reduce the risk of limb lymphedema as measured by other metrics of clinical lymphedema, including limb volume, skin thickness measurements, bioimpedance spectroscopy. To determine if the use of LYMPHA in breast cancer patients undergoing axillary lymphadenectomy will improve quality of life, as measured by limb-lymphedema-specific quality of life (LYMQOL) tool.

2. BACKGROUND

2.1 Study Disease

Lymphedema is a chronic, progressive, and debilitating condition that occurs with disruption or obstruction of the lymphatic system. Normally, lymphatics drain fluid from the interstitium that is not reabsorbed by venous capillaries [1]. When this drainage system doesn't function, lymphatic fluid accumulates, causing edema. Ultimately, this results in a limb that is heavy, painful, less functional, and at greater risk of infection and even malignant transformation [2]. Additionally, lymphedema significantly decreases quality of life [3, 4].

Lymphedema can be congenital (primary) or acquired (secondary). Secondary, or acquired, lymphedema is more common than primary lymphedema [1]. Worldwide, the most common cause of secondary lymphedema is infection and subsequent obstruction of the lymphatic system by *Wuchereria banrofti* [5]. In the United States, upper extremity lymphedema is commonly the result of the surgical and radiation therapy for breast cancer [2]. A large meta-analysis elucidated that roughly 1 in 5 women that survive breast cancer in North America will develop lymphedema [6]. Reported risk factors for developing lymphedema after sentinel lymph node biopsy (SLNB) is 3-6%, after axillary lymph node dissection (ALND) is 16-27% and as high as 40% after ALND and radiotherapy [6].

The standard of care for lymphedema continues to be conservative therapy, which includes manual decongestive therapies and compressive bandaging. Unfortunately, these conservative therapy modalities are inconvenient and tend to result in poor patient adherence [7].

Surgical options for lymphedema include physiologic surgeries and de-bulking procedures. Physiologic lymphedema surgery attempts to restore anatomic lymphatic flow. Specifically, this includes lymphovenous bypass and vascularized lymph node transfer. Physiologic surgeries are

A Randomized Clinical Trial of the LYMPHA procedure for the Prevention of Lymphedema after Axillary Lymphadenectomy

especially effective if performed before there is chronic fibrotic change in the affected limb [8]. Debulking procedures, such as suction assisted lipectomy and the modified Charles procedure are more suited for late stage lymphedema, after the lymphedematous tissue has remodeled, producing a large fibrotic component [9]. Unfortunately, these are highly morbid and mandate lifetime use of compression garments to prevent redevelopment of lymphedema [10].

Currently, there is no cure for lymphedema and the available therapeutic options are less than satisfying, prompting the investigation of prophylactic measures. Immediate lymphatic reconstruction, the LYMPHA (Lymphatic Microsurgical Preventative Healing Approach) technique, is one promising prophylactic intervention.

2.2 Study Agent/Device/Procedure

Immediate lymphatic reconstruction, termed LYMPHA or Lymphatic Microsurgical Healing Approach, involves anastomosing lymphatics to nearby veins distal to the site of injury to facilitate normal lymphatic drainage [11]. LYMPHA was first described by Boccardo et al [11]. In their series of 74 patients who underwent immediate lymphatic reconstruction at the time of axillary lymph node dissection (ALND), the reported rate of lymphedema was 4% at 4 years [12]. This is in contrast to the reported incidence of lymphedema after axillary lymph node dissection alone, which ranges from 13-65% [13-16].

These initial findings have since been supported by other groups. Hahamoff et al decreased their institution rate of lymphedema after ALND from 40% to 12.5% when paired with LYMPHA [17]. Feldman et al reported a 12.5% lymphedema rate after ALND and LYMPHA [18]. Johnson et al recently performed a meta-analysis to assess the impact of LYMPHA after ANLD and found that in incidence of lymphedema after ALND and radiation was 33.4% compared to 10.3% in those who underwent ALND, radiation, and LYMPHA [19].

The body of the referenced data suggests that LYMPHA is a viable modality for the prevention of lymphedema. However, to date, there are no randomized clinical trials evaluating the efficacy and safety of this procedure. Therefore we suggest initiating a randomized clinical trial to more accurately elucidate the role of the LYMPHA procedure in the prevention of lymphedema after axillary lymphadenectomy.

For clinicaltrials.gov compliance

The LYMPHA procedure is not a drug so this does not apply.

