12.6.2 Sample size justification

The risk of lymphedema development is considered to be 30% in the surgical control group (group A), and studies have shown it is to be reduced to 4% when LYMPHA is applied during an axillary lymphadenectomy [12, 30]. With N=40 subjects (20 subjects per arm A and C) in the first stage, the power to stop after the first stage is 56%. Finally, with additional N=40 subjects (20 subjects per arm A and C) in the second stage, the overall power to stop at either the first or the second stage is 88%.

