12.6.3 Effect size justification

The effect size used in the previous subsection was based on the study conducted by Boccardo et al, in which 74 patients underwent LYMPHA procedure after axillary lymph node dissection [12]. The incidence of lymphedema in the cited cohort after the LYMPHA procedure was 4.05%. Comparatively, the incidence of lymphedema after axillary lymph node dissection ranges from 13-65% [13-16]. This study provides a reasonable baseline for comparison to as it includes the same target population (women undergoing axillary lymphadenectomy related to breast cancer) and shows a substantially lower incidence of lymphedema compared to other literature.

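### The 88% power in section 12.6.2 rests on the lowest of the four LYMPHA rates in section 2.2 and on a 20 + 20 per arm design; at the current 30 per arm, Fisher's test gives 69% even at 30% v 4%, and 27% to 60% at the other cited rates

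*Protocol*

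**What the plan says.** Section 12.6.2 sets the control rate: "The risk of lymphedema development is considered to be 30% in the surgical control group (group A"). For LYMPHA it says that "studies have shown it is to be reduced to 4% when LYMPHA is applied during an axillary lymphadenectomy". With 20 per arm in a first stage and 20 more per arm in a second, it states 56% power to stop at stage one and 88% overall.

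Section 12.6.3 names the source of the effect size, a single series of 74 LYMPHA patients: "The incidence of lymphedema in the cited cohort after the LYMPHA procedure was 4.05"%. It gives 13% to 65% as the range after dissection alone, and says the series "shows a substantially lower incidence of lymphedema compared to other literature".

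Section 2.2 reports the same series ("the reported rate of lymphedema was 4% at 4 years") and three other LYMPHA results:
- one group changed its "institution rate of lymphedema after ALND from 40% to 12.5% when paired with LYMPHA";
- another "reported a 12.5% lymphedema rate after ALND and LYMPHA", with no comparator given;
- in a meta-analysis, incidence "after ALND and radiation was 33.4% compared to 10.3% in those who underwent ALND, radiation, and LYMPHA".

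Sections 2.4, 3.4 and 12.1.1 describe the current recruitment as a new three-arm phase of 90 subjects allocated 1:1:1, so 30 per arm. Section 12.4.2 plans Fisher's exact test for LYMPHA against dissection alone, and section 12.1 sets a 5% significance level. Section 12.6.2 gives no power at any other pair of rates or at 30 per arm.

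**The concern.** The power statement has two weak supports.

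The first is the LYMPHA rate. The wording of 12.6.2 suggests that several studies agree on about 4%. In the protocol's own review only one of the four LYMPHA results is near 4%. The others are 10.3/4 = 2.6 and 12.5/4 = 3.1 times as high. Power depends heavily on this input, yet no alternative is shown.

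The second is the design. The 56% and 88% are for two stages of 20 per arm, whereas the phase now recruiting has 30 per arm.

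At stake is what the sponsor, the review committees and later readers believe the trial can detect. A fall from 33.4% to 10.3% removes about two thirds of the risk ((33.4 − 10.3)/33.4 = 69%). The text implies that the trial is well placed to detect a benefit, but an effect of that size would be missed about half the time at 30 per arm.

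**Working it through.** **Inputs.** Control 30%, LYMPHA 4%, stages of 20 + 20 per arm (12.6.2); 5% level (12.1); other rates from 2.2; 30 per arm (2.4); Fisher's exact test (12.4.2). The protocol states neither the stopping boundary nor whether the test is two-sided.

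**Step 1: reproduce 56% and 88%.** I used a two-look z-test with unpooled variance, a two-sided 5% Pocock boundary of 2.178 at both looks, and correlation √0.5 between looks. The expected z at look k is θ_k = (p_A − p_C) / √{[p_A(1 − p_A) + p_C(1 − p_C)] / n_k}, with n_1 = 20 and n_2 = 40 per arm.

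For 30% v 4%:
- the variance sum is 0.21 + 0.0384 = 0.2484;
- θ_1 = 0.26/√(0.2484/20) = 2.333 and θ_2 = 0.26/√(0.2484/40) = 3.299;
- power at look one is Φ(2.333 − 2.178) = Φ(0.155) = 56.2%;
- the bivariate normal probability of crossing at either look is 88.2%.

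Both stated figures reproduce. A two-sided O'Brien-Fleming boundary gives 32% and 91%, and a one-sided 5% Pocock boundary gives 68% and 93%, so neither fits. A Lan-DeMets Pocock-type boundary (57.0% and 87.8%) is also close. The boundary is therefore an inference.

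**Step 2: change only the rates, then change the design to the current one.** The last column is exact two-sided Fisher power at 5%: the sum, over all pairs of event counts with Fisher p ≤ 0.05, of Bin(30, p_A) × Bin(30, p_C), with no dropout.

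| Control v LYMPHA | Basis | Two-stage, 20 + 20 per arm | Fisher, 30 per arm |
|---|---|---|---|
| 30% v 4% | 12.6.2 | 88.2% | 68.9% |
| 33.4% v 10.3% | within one source (irradiated patients) | 69.2% | 47.6% |
| 40% v 12.5% | within one source | 79.7% | 59.7% |
| 30% v 10.3% | 12.6.2 control, 2.2 LYMPHA rate | 56.8% | 35.8% |
| 30% v 12.5% | 12.6.2 control, 2.2 LYMPHA rate | 45.0% | 27.1% |

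**Step 3: does the result depend on the inferred boundary?** A single look at 40 per arm with Fisher's test needs no boundary. It gives 87%, 65%, 76%, 52% and 40% for the five rows, so the same fall appears.

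**Step 4: precision of the 4%.** 4.05% of 74 is 3 events (3/74 = 4.05%). The exact 95% confidence interval is 0.8% to 11.4%.

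**The case against.** The strongest reply is that nothing is hidden. Section 12.6.3 says openly that the effect size comes from one 74-patient study, and section 2.2 prints the higher rates. That stands: this is a disclosed, favourable planning assumption, and a reader should not infer concealment. Nor do the sources show that 4% is wrong. The interval from 3 events reaches 11.4% and so includes 10.3%. The sizes behind the two 12.5% reports are not given, and overlap between the meta-analysis and the separate series cannot be checked, so one in four is not a count of equal, independent votes.

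The alternatives also have limits. The 30% v 10.3% and 30% v 12.5% rows combine rates from different sources. The 33.4% v 10.3% pair is in irradiated patients. Section 3.2 excludes axillary radiotherapy before surgery and nodal radiation less than 4 weeks after it, while section 4.1 excludes concomitant radiotherapy, so how well that pair matches the trial population is unclear.

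Three stronger readings are tempting but not supported:
- That 12.6.3 admits choosing the most favourable LYMPHA series. The preceding sentence compares with dissection alone, so the other literature there most naturally means those rates.
- That a 4-year rate is too optimistic for a Month 12 endpoint. If incidence accumulates, the 12-month rate under the same definition would be no higher than the 4-year rate.
- That a non-significant result will be presented as a failure of LYMPHA. No section says so.

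Finally, the 88% comes from a design that the three-arm phase has replaced. That is true, but 12.6.2 still presents it as the justification, so it strengthens the case for restating the power.

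**Conclusion.** The point holds as a correction to the stated power and its wording. The plural attribution in 12.6.2 is not borne out by section 2.2: the 4% comes from one series and is the lowest of the four LYMPHA rates cited. The 88% is reproducible for 20 + 20 per arm at 30% v 4%. On that plan it falls to 69% and 80% at the two within-source pairs, and to 57% and 45% with control held at 30%. In the current phase it is not reached even at 30% v 4% (69%); the other four pairs give 48%, 60%, 36% and 27%.

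The two-stage figures rest on the inferred two-sided Pocock boundary. The Fisher figures assume a two-sided 5% test, 30 evaluable patients per arm, no dropout, and no pooling of the 27 patients from the two-arm phase, whose data section 12.2 assigns to a preliminary assessment. If they were pooled, the arms would be 13 + 30 = 43 and 14 + 30 = 44 as randomized, near the 40 per arm of Step 3. Power would then be about 87% or slightly more at 30% v 4%, but still well short of 88% at the other pairs.

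**What to change.** In section 12.6.2:
- Replace the attribution to studies in the plural with a statement that 4% comes from one series of 74 patients and is the lowest of the four LYMPHA rates in section 2.2.
- Replace the 56% and 88% with Fisher power at 30 per arm: 69% at 30% v 4%. Beside it show the within-source pairs, 48% at 33.4% v 10.3% (noting that this pair is in irradiated patients) and 60% at 40% v 12.5%, and the pairs with control at 30%, 36% at 10.3% and 27% at 12.5%.
- State that these figures are two-sided at 5% and make no allowance for dropout.

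Add a cross-reference in section 12.6.3 to the other LYMPHA results in 2.2. Keep the sample size. The cost is a few sentences and a small table; the downside is a less favourable stated power.

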2.3 Rationale

As reviewed in sections 2.1 and 2.2, lymphedema is a progressive and debilitating disease that significantly affects quality of life. Current therapeutic options for lymphedema are less than optimal. Manual decompressive therapy is highly inconvenient with poor patient adherence, physiologic surgeries are most effective in early lymphedema, and debulking procedures are morbid. Given that 1 in 5 women tend to develop lymphedema after surviving breast cancer, a prophylactic therapy would be advantageous. The LYMPHA procedure is one prophylactic modality that has promising results as reviewed above. We propose a clinical trial to more

A Randomized Clinical Trial of the LYMPHA procedure for the Prevention of Lymphedema after Axillary Lymphadenectomy

accurately evaluate the role of LYMPHA in preventing lymphedema after axillary lymphadenectomy.

2.4 Study Design

We propose a randomized clinical trial to determine the efficacy of the LYMPHA procedure in breast cancer patients undergoing axillary lymphadenectomy.

Up to 100 subjects will be enrolled in the trial; they will undergo either lymphadenectomy, lymphadenectomy with soft tissue reinforcement (STR) or lymphadenectomy with LYMPHA. Subjects must meet all additional defined inclusion and exclusion criteria.

Please note that soft tissue reinforcement is common practice and used as the standard of care in some lymphedema centers. The addition of this group is important because it allows a comparison of LYMPHA to a currently commonly practiced alternative and the ability to assess for superiority of the LYMPHA procedure. In short, at Stanford, we perform soft tissue reinforcement with collagen scaffolding commonly and would like to start including these patients in our prospective analysis/study.

All patients that are enrolled will be randomized into one of three groups: Group A (surgical control group 1) – the patients will undergo lymphadenectomy alone with simple wound closure, Group B (surgical control group 2) – the patients will undergo lymphadenectomy with soft tissue reinforcement using a collagen scaffold, or Group C (treatment group) - the patients will undergo lymphadenectomy and LYMPHA at the time of wound closure as an adjunct to lymphadenectomy procedure.

Randomization will occur after it has been determined that patients are eligible for the trial intraoperatively. Patients are deemed eligible for the trial intraoperatively if ALND is performed and there are available lymphatics to bypass.

The study will be double blind and randomized. Each patient will be randomized to either the treatment or control group 1 or 2 and will be blinded to their group. While the surgeons will not be blinded, all personnel who track outcomes in clinic will be blinded. The primary outcomes that the protocol is designed to evaluate include efficacy, safety, and impact on the quality of life.

The study was started with 2-arm design (Group A and Group C). A preliminary assessment to the trial effects will be conducted using the current collected data. After the revised protocol is approved, the study will recruit subjects in the new 3-arm phase: 90 subjects (30 subjects per arm in the three groups (Groups A, B, C)

2.5 Correlative Studies Background

We plan to investigate the use of the LYMPHA procedure in decreasing the risk for lymphedema and improving quality of life after axillary lymphadenectomy. As reviewed in section 2.2, this procedure has been shown to reduce the incidence of lymphedema compared to ALND alone in prospective cohort studies, however, no randomized clinical trial has been conducted to confirm this observation.

3. PARTICIPANT SELECTION AND ENROLLMENT PROCEDURES

3.1 Inclusion Criteria

- 3.1.1 Ages 18 to 75 years (inclusive)
- 3.1.2 Patients undergoing unilateral breast cancer related axillary lymphadenectomy
- 3.1.3 Free of distant metastasis in preoperative screening
- 3.1.4 Histology results of axillary lymph nodes could be either Negative or Positive
- 3.1.5 Patients who undergo preoperative chemotherapy can be included
- 3.1.6 Willingness and ability to provide written informed consent
- 3.1.7 Willingness and ability to comply with all study procedures
- 3.1.8 Preauthorization for ALND with LYMPHA is received
- 3.1.9 ALND is performed during surgery and there are available lymphatics for bypass

3.2 Exclusion Criteria

- 3.2.1 Primary lymphedema of the affected upper limb
- 3.2.2 Secondary lymphedema of the affected limb prior to the lymphadenectomy
- 3.2.3 Radiotherapy at the axilla before the study / surgery
- 3.2.4 Allergic reaction to porcine collagen or ICG
- 3.2.5 Receiving radiation therapy to the involved nodal basin in a period less than 4 weeks after the surgery
- 3.2.6 Concurrent participation in a clinical trial of any other investigational drug or therapy, regardless of indication, within 1 month before screening
- 3.2.7 Other medical condition that could lead to limb edema, such as (but not limited to primary lymphedema or acute venous thrombosis

A Randomized Clinical Trial of the LYMPHA procedure for the Prevention of Lymphedema after Axillary Lymphadenectomy

3.2.8 Other medical condition that could result in symptoms overlapping those of lymphedema in the affected limb (e.g., pain, swelling, decreased range of motion)

3.2.9 Either of the following, at the time of baseline evaluation: ipsilateral:contralateral limb volume ratio >1.1 or R0 bioimpedance ratio > 1.106 when the nondominant limb is at risk, and 1.134 when the dominant limb is at risk.

3.2.10 Life expectancy < 2 years for any reason

3.2.11 Pregnancy or nursing

3.2.12 Substance abuse (such as alcohol or drug abuse) within 6 months prior to screening

3.2.13 Severe psychiatric disease

3.2.14 Significant or chronic renal insufficiency (defined as serum creatinine > 2.5 mg/dL or an estimated glomerular filtration rate [eGFR] < 30 mL/min at screening) or requires dialytic support

3.2.15 Hepatic dysfunction, defined as alanine transaminase (ALT) or aspartate transaminase (AST) levels $> 3 \times$ upper limit of the normal range (ULN) and/or bilirubin level $> 2 \times$ ULN at screening

